7.2 Setting

This is a non-interventional study and does not impose a therapy protocol, diagnostic/therapeutic procedure, or a visit schedule. Patients will be treated according to the local prescribing information and routine medical practice in terms of visit frequency and types of assessments performed and only these data will be collected as part of the study.

Every effort will be made to enroll all patients treated with voretigene neparovec, and it is expected that a minimum of 40 adult or pediatric, male or female patients can be enrolled over a five year enrollment period. Patients will be followed for five years following administration of voretigene neparovec.

Patients will be enrolled based on the selection criteria described below. Participation in the study is voluntary but strongly encouraged to enroll all patients treated with voretigene neparovec.

Selection criteria:

1. Is planning to receive or has received voretigene neparovec in at least one eye.
2. Provided informed consent/assent to participate in this study.
3. Has not previously participated and is not currently participating in an interventional clinical trial with voretigene neparovec.

Patients who planned to be treated or have been treated with voretigene neparovec will be informed of this study by qualified study sites. After informed consent/assent is provided, data (including any relevant pre-existing data collected prior to informed consent) will be collected in this registry-based study.

Qualified study sites will be primarily Luxturna[®] treatment centers where qualified staff (i.e., vitreoretinal surgeons and pharmacists) have participated in the mandatory educational program about use of the product, and inherited retinal dystrophy (IRD) referral centers. Preferably, patients are followed up at the same Luxturna[®] treatment center or IRD referral center where they were enrolled, for consistency of data collection. If more than one center is involved in the

treatment and follow-up of a patient (e.g. a treatment center and a referral center), then enrollment into the study should take place at the site where the patient will be seen most frequently and data from all other centers will be collected at this study site.

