For all patients, additional data should be collected in the study at a minimum on an annual basis after treatment, including AESI/AE/SAEs, pregnancy occurrence and outcomes (in patient and female partners of patient), concomitant medications and procedures, patient-reported outcome questionnaires, caregiver questionnaires, and post-administration ophthalmic examinations. Study sites will be provided with a list of questions regarding AESIs to standardize safety data collection as much as possible (refer to Safety Questionnaire in [Section 12.1](#)). At each visit the patient should be specifically questioned and evaluated on each of these AESIs. Additionally the patient should also be asked whether they have had any other AEs, SAEs or whether they or their partner has been pregnant during the period since the last visit. Any findings will be entered on the AE eCRF.

Data may be collected in the study more frequently, as safety events become known for an individual patient. Qualified site personnel may obtain data from the patient at any time via other forms of contact such as telephone, e-mail or postal mail. Patients should be encouraged to return to the same study site for their follow-up. Data may be sourced from the study site, other treating physicians (e.g. primary physicians, local/primary ophthalmologists, and ophthalmic surgeons), patient, or patient caregivers (e.g. family members, home nursing).

In addition, patients and their physicians will be instructed to contact the study site any time an AESI/AE/SAE, pregnancy occurrence or pregnancy outcome (in patient and female partners of patient) becomes known. Each enrolled patient will be given a patient/care provider card noting s/he has been treated with voretigene neparvovec and is participating in this study. The patient/care provider card should be shown to any health care practitioner treating the patient in order to facilitate the reporting of safety events and pregnancy occurrence (in patient and female partners of patient).

If the study site staff becomes aware of an adverse event in a study patient at any time, or a pregnancy in a patient or female partner of a patient, those data are to be reported as per the study reporting timelines ([Section 9.1](#)).

Patients may withdraw from the study at any time without prejudice to their care. For patients who discontinue prematurely, the reason for discontinuation should be determined.

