A patient will be considered potentially lost to follow-up if they do not return to the study site for the annual follow-up visits and no information can be obtained via telephone contact or other sources. The site is encouraged to make every effort (phone, email, certified mail) and document those efforts to regain contact to resume data collection. A patient cannot be considered as lost to follow-up until the time point of their scheduled End of Study visit has passed.

Variables

The safety profile of voretigene neparvovec, administered to patients who enroll in this study, should be evaluated based on the examination of general demographic and safety variables, including specific clinical measures.

Pre-treatment and Baseline characteristics

- Demographics (e.g. age, gender, race, ethnicity, and country of residence)
- Medical and surgical history (including prior gene and cell therapy)
- Ocular characteristics (including information on viable cells and ophthalmic exam results)
- Genetic diagnosis related to the inherited retinal dystrophy
- Clinical diagnoses related to the inherited retinal dystrophy
- Concomitant medications and procedures
- PRO and caregiver questionnaires

Voretigene neparvovec administration information

- Surgical center location
- Date of injection(s) (right eye, left eye)
- Lot number and volume administered (right eye, left eye)
- Details of perioperative corticosteroids use
- Surgical details including number and location of retinotomies (right eye, left eye)

Safety Variables

- The following events are designated as AESIs and will be queried through the standardized safety questionnaire ([Section 12.1](#)) and entered into the AE CRF:
 - Ocular AEs
 - Lack of efficacy and/or decline in efficacy over time*
 - Third-party transmission
 - Host immune response
 - Development or exacerbation of oncologic, hematologic, neurologic, or auto-immune diseases
- ***Note:** Signs and symptoms resulting from “lack of efficacy” or “decline of efficacy over time” or “failure of expected pharmacological action” should be provided in the AE or SAE description.
- Follow-up information on reported chorioretinal atrophy
- Any other AEs and SAEs
- Information on pregnancy occurrence, outcomes, and lactation (from patients and female partners of patient)
- Ophthalmic examination results for VA, VF, FST, and OCT:

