7.6 Data analysis

This study is intended to descriptively document the frequency and severity of events of interest related to voretigene neparovec (vector and/or transgene), the subretinal injection procedure, the concomitant use of corticosteroids, or a combination of these procedures and products. The Full Analysis Set (FAS), defined as all individuals for whom an informed consent/assent was signed and who are enrolled in the study and received at least one injection of voretigene neparovec, will be used to summarize all data.

Continuous variables will be summarized in terms of mean, standard deviation, median, minimum and maximum. Other descriptive statistics (e.g., quartiles, coefficient of variation) may be reported when appropriate. Categorical variables will be summarized using frequency

counts and percentages. Unless otherwise noted, the denominator for the percentages will include all patients in the FAS population.

The unit of analysis for disposition, demographics and baseline diagnoses will be patient; the unit of analysis for ophthalmic examination findings will be right eye and/or left eye. The unit for non-ocular AEs will be patient; the unit for ocular AEs will be eye(s). The unit for other variables will be patient or eye(s) as appropriate.

Analyses to assess the impact of subgrouping based on selected variables which become of interest during the study will be performed as defined in the Statistical Analysis Plan (SAP).

Interim data assessments will occur at a minimum, on an annual basis and will be included in annual progress reports. A complete description of the statistical analyses and methods will be available in the SAP.

7.6.1 Demographics, baseline disease characteristics, disposition, ophthalmic examination findings, and other variables

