Descriptive summary statistics will be provided for demographics and pre-treatment/baseline disease characteristics. Descriptive summary statistics will also be provided for ophthalmic examination results (e.g., VA, VF, FST, and OCT) at pre-treatment/baseline and post-administration. Ophthalmic examination results will be presented by age categories. Patient- and caregiver-reported outcomes will be summarized at pre-treatment/baseline and annually for questionnaire overall and subscale scores presented as percentages. Disposition, including number of patients enrolled in the study at the time of each analysis, will be tabulated; demographic characteristics will also be re-summarized at each analysis point.

The unit of analysis for disposition, demographics and pre-treatment/baseline diagnoses will be patient; the unit of analysis for ophthalmic examination findings will be right eye and/or left eye. The unit for non-ocular AEs will be patient; the unit for ocular AEs will be eye(s). The unit for other variables will be patient or eye(s) as appropriate.

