7.6.2 Voretigene neparvovec safety

Adverse events including the AESIs, SAEs, and pregnancy occurrence and outcome information (including information collected in the Novartis Global Safety database) will be summarized in annual progress reports and the final study report. All AEs and SAEs will be provided in patient data listings. Additional listings, summaries, and graphics may be generated, as appropriate.

Adverse events will be coded to system organ class (SOC) and preferred term (PT) using the Medical Dictionary for Regulatory Activities (MedDRA). The incidence (number and percentage of patients with an AE observed one or more times) and number of events for each AE will be presented for AEs and SAEs, and will be tabulated by SOC and PT, both overall and by severity level and relationship to treatment and/or surgical procedure, as appropriate. This will be performed both for the cumulative duration of follow-up through the analysis time point of interest and/or on an annual basis, the latter to assess the potential, if any, for increasing or decreasing trend in reported AEs. Safety results will be presented by age categories.

Administration of voretigene neparvovec includes the surgical procedures of pars plana vitrectomy followed by voretigene neparvovec injection via bleb formation in the subretinal space. AEs associated with the administration procedures include: increased intraocular pressure, retinal tear, retinal detachment, macular disorders, cataract, and intraocular inflammation and/or infection related to the procedure. A comparative analysis of these ocular AEs between treated patients and published literature data on pars plana vitrectomy will be included in the progress reports.

The incidence of these identified AEs will be summarized descriptively for this study.

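### Out-of-contact patients stay in the all-FAS denominator of the adverse-event percentages, so later annual and cumulative figures can be too low and a constant risk can look like a falling one.

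*Protocol*

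**What the plan says.** **Follow-up status (protocol 7.2).** Follow-up is fixed at five years: "Patients will be followed for five years following administration of voretigene neparovec". The final loss status is held back to the end of that period: "A patient cannot be considered as lost to follow-up until the time point of their scheduled End of Study visit has passed". An interim status exists in the same paragraph: "A patient will be considered potentially lost to follow-up if they do not return to the study site for the annual follow-up visits" and nothing can be learned by telephone or from other sources. Patients may also withdraw at any time, and "For patients who discontinue prematurely, the reason for discontinuation should be determined".

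**Disposition (7.6.1).** "Disposition, including number of patients enrolled in the study at the time of each analysis, will be tabulated". Neither the number still under observation nor the number potentially lost is named.

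**Denominator (7.6).** "Unless otherwise noted, the denominator for the percentages will include all patients in the FAS population".

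**AE measure (7.6.2).** "The incidence (number and percentage of patients with an AE observed one or more times) and number of events for each AE will be presented", both for cumulative follow-up and/or by year, the yearly presentation serving "to assess the potential, if any, for increasing or decreasing trend in reported AEs".

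**The concern.** Each provision is reasonable alone. Holding back the final loss label keeps sites trying to reach the patient, and an all-FAS percentage is a common default. The difficulty is the combination. The interim status is defined for sites but has no stated place in the tables. The percentages divide by everyone treated and enrolled, whether or not anyone has heard from them in the period.

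The trend reading is the most exposed use. If contact thins out over five years, yearly percentages on a fixed denominator fall even when the risk among patients is unchanged. A reader of the annual progress reports, which go into the PSUR, could take this as a risk that wanes after treatment. For late events, which a five-year safety registry exists to find, the error is in the reassuring direction.

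**Working it through.** **Inputs.** From the protocol: five years of follow-up, an expected minimum of 40 patients, the all-FAS default denominator and the crude percentage. The protocol states no loss rate, event rate or precision target, so there is no figure of its own to reproduce. Assumed here: a fraction *q* of patients falls silent each year (2% to 20%); a constant annual risk *h* = 5%; silence unrelated to events; an event in year *k* becomes known only if the patient is reached at annual visit *k*; all 40 patients are already five years past treatment, so that silence is the only effect at work.

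**Patients reached at Year 5:** 40(1−*q*)^5. With *q* = 5%: 40 × 0.7738 = 31.0, so 9.0 of 40 are silent.

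**Annual percentage on the FAS in year *k*:** *h*(1−*q*)^k. With *q* = *h* = 5%, years 1 to 5 give 4.8%, 4.5%, 4.3%, 4.1% and 3.9%. The risk is 5% in every year; the decline comes from silence alone. Divided by patients reached, every year gives 5%.

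**Five-year cumulative percentage** (here *h* is the annual risk of a first event):
- Complete follow-up: 1 − 0.95^5 = 22.6%.
- On the FAS: Σ *h*(1−*h*)^(k−1)(1−*q*)^k = 0.0475 × (1 − 0.9025^5)/(1 − 0.9025) = 0.0475 × 0.40126/0.0975 = 0.19549, or 19.5%. The relative shortfall is 1 − 19.55/22.62 = 14%.

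**Range over the assumed rate of silence, *h* = 5%:**

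| *q* per year | Reached at Year 5 (of 40) | Year-5 annual % on FAS (true 5%) | 5-year cumulative % on FAS (true 22.6%) |
|---|---|---|---|
| 2% | 36.2 | 4.5 | 21.3 |
| 5% | 31.0 | 3.9 | 19.5 |
| 10% | 23.6 | 3.0 | 16.9 |
| 15% | 17.7 | 2.2 | 14.5 |
| 20% | 13.1 | 1.6 | 12.4 |

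**Other settings.** With *h* = 10% and *q* = 5%, a true 41.0% reads 35.6%. If instead every event up to the moment of silence is captured, use constant hazards λ = −ln 0.90 and μ = −ln 0.95. The reading is then λ/(λ+μ) × (1 − e^(−5(λ+μ))) = 36.5%. The direction is the same and the shortfall slightly smaller.

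**Zero events.** The one-sided 95% upper bound is 1 − 0.05^(1/n): 7.2% on 40 patients but 9.2% on 31.0. The full FAS count overstates what an absence of events can exclude in Year 5.

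**Does the label matter?** Suppose the silent patients were called lost at month 15 and the FAS denominator were kept. They would still be in the FAS, so no percentage above would change. The bias comes from the denominator together with the crude measure. The final-status rule affects only what the disposition table can show.

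**The case against.** The strongest reply is that the protocol already has an interim status, that withdrawal with a reason is recorded, and that the all-FAS denominator applies only unless otherwise noted. The full methods and the handling of missing data are deferred to a SAP that is not at hand, and the SAP may set another denominator or a censoring rule. The disposition sentence gives an example rather than a closed list. Section 7.2 also allows information from other physicians, caregivers, telephone, e-mail and post, so a missed visit is not always a gap in knowledge.

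Much of this stands, and it rules out a stronger reading that a reader might infer: that silent patients must appear as ongoing and event-free in every annual report, with no loss visible until Year 5. The documents do not say that. The interim status could be tabulated, events before silence stay counted, and outside sources can supply later ones. Patients treated before study start are also eligible, and their five years run from administration, so some can reach the end-of-study date earlier than those treated after it. Nor does the final-status rule itself cause the low percentages, as the last step of the check shows.

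What the reply does not remove is the default. The protocol itself states the denominator, the crude measure and the trend purpose, and it gives the interim status no role in any of them.

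**Conclusion.** The point holds as a fault in the stated analysis defaults. On the all-FAS denominator, annual and cumulative AE percentages can be too low once patients are out of contact, and the yearly series can show a decline that is not there. At an assumed 5% silent per year and 5% annual risk, the Year-5 figure reads 3.9% instead of 5%, and the cumulative figure 19.5% instead of 22.6%. At 2% silent the effect is small (21.3%); at 10% it is about a quarter of the true cumulative value (16.9%).

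These sizes rest on assumed rates, on silence being independent of events, and on no information arriving from elsewhere. If silent patients differ in risk, the error could be larger or smaller. The SAP may already set another denominator, in which case the protocol text should be brought into line with it. The matter should be settled before the yearly series is read for trends.

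**What to change.** Keep the re-contact duty and the final-status rule in 7.2.

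- **In 7.6.1:** at each annual cut, tabulate patients under observation, patients potentially lost (defined by a pre-set window since the last information from any source), patients withdrawn and patients who completed. A patient who is reached again returns to under observation.
- **In 7.6.2:** keep the crude FAS counts. Base the annual and cumulative AE incidence on patients or person-time actually observed, censored at the date of last information. For ocular events, where 7.6 makes the eye the unit, apply the same rule to eyes. Show the number observed beside each yearly percentage, and state that censoring assumes similar risk in those no longer reached.

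Under the assumptions above, the observed-patient denominator returns the Year-5 figure from 3.9% to 5%. The cost is a short amendment to two sections, a derived last-information date, and slightly more analysis. Reported attrition and AE frequency will look less favourable. Sites and patients need do nothing new, provided that the date of each contact is recorded.

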7.3 Data sources

Data sources for the collection of safety variables, demographics, pre-treatment/baseline characteristics, and surgical details will include medical notes, electronic medical records, and hospital discharge files documented during routine care or may be derived from ocular assessments including VA, VF, FST, and OCT. AESIs will be collected using a standardized safety questionnaire. Patient- and caregiver-reported outcomes will be collected through questionnaires from patients and caregiver, respectively.

Safety data will be transferred to Novartis at a frequency as defined in [Section 9](#) of this protocol and/or CRO contract.

Data collection schedule

This is a non-interventional study which does not impose a therapy protocol, diagnostic/therapeutic procedure, or a visit schedule. Patients will be treated according to the local prescribing information, and routine medical practice in terms of visit frequency and types of assessments performed and only these data will be collected as part of the study. The treating physician is asked to complete – if possible – the appropriate CRF at every patient visit.

However, in addition to the questionnaires, below is the minimum recommended data collection schedule that most likely aligns with the patterns of routine clinical care of patients being treated with voretigene neparvovec.

Table 7-1 Data collection

Assessments	Pre-treatment/ baseline data collection point	Post- treatment data collection point	Follow-Up data collection point (Years 1-5)
Signed informed consent/assent	To be completed prior to data collection		
Eligibility assessment	To be completed prior to data collection		
Demographics (age, gender, race, ethnicity, and country of residence)	X		
Medical and surgical history (including prior gene and cell therapy)	X		
Ocular characteristics (including information on viable cells and ophthalmic exam results)	X		X
Genetic diagnosis related to inherited retinal dystrophy	X		
Clinical diagnoses related to inherited retinal dystrophy	X		
Concomitant medications and procedures	X ^a	X	X
Date of injection(s) (right eye, left eye), Treatment center that treated patient, & treatment funding source (country)		X	
Lot number, expiry date, and volume administered (right eye, left eye). Perioperative steroid use.		X	
Surgical details including number and location of retinotomies (right eye, left eye)		X	
For patients enrolled under protocol version 01			
mVFQ-25 (Section 12.2)	X ^b		X
For patients enrolled under protocol version 02			
For all protocol versions			
BIC (Section 12.5)	X ^b		X
Safety Variables			
Ophthalmic examination: visual acuity (VA), visual field (VF), full-field light sensitivity threshold testing (FST), and optical coherence tomography (OCT)	X ^c		X
All AEs of special interest (AESIs): ocular AEs, lack of efficacy and/or decline of efficacy over time, third-party transmission, host immune response, and development or exacerbation of oncologic, hematologic, neurologic, or auto-immune diseases (NOTE: Collection must be assessed at each visit in accordance with the standardized safety questionnaire)		X	X

Assessments	Pre-treatment/ baseline data collection point	Post- treatment data collection point	Follow-Up data collection point (Years 1-5)
Any other AEs or SAEs		X	X
Pregnancy occurrence and outcomes (from both patient and female partners of patient), including whether any child was breastfed		X	X
End of study visit			X

a - Concomitant medications taken and procedures performed within 30 days prior to voretigene neparovec treatment.

b - Baseline questionnaire to be completed prior to voretigene neparovec treatment.

c - Most recent ophthalmic examinations performed within 3 months prior to voretigene neparovec treatment.

